Objectives	
Primary Objective:
 
To assess if alterations of the microbiota in the maternal gut (dysbiosis) is associated with maternal gestational weight gain.
 
To determine the association between maternal microbiome dysbiosis during pregnancy and birth outcomes, infant growth, infant nutritional status and health in the first year of life.
 
Secondary Objectives:
 
To link the maternal microbiome to dietary intake, with a focus on calories and macronutrients.
 
To integrate maternal anthropometric factors, morbidity and mortality with microbiome data to reveal key modulators (microbial taxa and metabolites) of dietary intake during pregnancy and the post-partum period.
 
To determine the impact of the maternal microbiome during pregnancy, including the exposure to pathogens and parasites, on the development of the infant microbiome.
 
To investigate the maternal microbiome's exposure to pathogens and parasites, and the association with intestinal inflammation.
 
Exploratory Objectives:
 
To explore the role of the maternal gut microbiome during pregnancy and to identify gut community dynamics in pregnant women and how this impacts differences between dietary intake and nutritional status.
 
To investigate socio-economic factors; including gender, poverty, exclusion and empowerment, and their influence on the health of a mother's microbiome (assessed by alpha and/or beta diversity, and absence of pathogens).
 
To explore the role of the human microbiota on nutritional status by performing fecal microbiota transplants in germ free mice and sterile piglets.

Recruitment and Follow-up	

1) MV1: 10-14 weeks post conception

2) MV2: 30-34 weeks post conception

3) MV3/ IV1: 24-72 hours after birth

4) MV4/IV2: 3 months post-partum

5) MV5/ IV3: 6 months post-partum

	6) MV6/IV4:12 months post-partum  MV: Maternal Visit IV: Infant Visit
Study Population:	Pregnant, married women aged 17 to 24 years from the Matiari district, Pakistan and their infants.
No. of Subjects	400 women and their infants. • 200 subjects with normal BMI (18.5-24.9) at conception • 200 subjects with low BMI (less than 18.5) at conception
Study Duration:	The study duration will be approximately 3 years.

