### 4.2 STUDY DESIGN

The study will be a prospective, longitudinal observational study to investigate the impact and relationship between prokaryotic and eukaryotic microbes in the gut and their association with maternal health and birth outcomes among young women, 17-24 years of age in Matiari District, Pakistan. The study will aim to recruit 400 women into two groups based on BMI at time of recruitment (Normal: BMI between 18.5 and 24.9 kg/m^2 and Low: BMI less than 18.5 kg/m^2, as defined by WHO guidelines[85]). Our goal is to recruit 200 participants with normal BMI and 200 participants with low BMI into the study. However, in the event that we have difficulty reaching this recruitment target, we will recruit more women into the normal weight BMI. The study will follow women and their infants over the course of their pregnancy and for a year post-partum, collecting stool and blood samples, nutritional information, health assessments, anthropometric measurements and empowerment metrics at different time points.

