## 9 STATISTICAL CONSIDERATIONS

### 9.1 POWER CALCULATION

The adequacy of the sample size was verified using the ‘pwr’ package (version 1.2-2) in R (version 3.6.1). Calculations were based on the correlation between  $\alpha$ -diversity (Shannon index) and weight gain during pregnancy. Assuming 400 participants are recruited into the study, and a type I error rate of 0.05, there will be 80% power to detect a correlation coefficient ( $r$ )  $>0.14$ . This is conventionally considered a small effect size[109]. Thus, we expect to be powered to reveal significant association between weight gain during pregnancy and diversity. Further, a study of 123 lean and 24 obese individuals, revealed 96% power to detect differences in Bacteroidetes abundance and 80% power for Firmicutes[110], while a cohort of 44 Malawian malnourished children was sufficient to detect significant differences in bacterial  $\alpha$ -diversity in the presence and absence of *Blastocystis*.

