#### 9.4.1 ADDRESSING THE PRIMARY OBJECTIVES

This study has two primary objectives: 1) To assess if alterations of the microbiota in the maternal gut (dysbiosis) are associated with maternal gestational weight gain; and 2) To determine the association between maternal microbiome dysbiosis during pregnancy and birth outcomes, infant growth, nutritional status and health status in the first year of life.

The first objective will be addressed through the following approaches. First, maternal gut bacteria and eukaryotic profiles will be used to calculate Bray-Curtis dissimilarity metrics between individual samples which will be leveraged in principal co-ordinate analyses to determine the extent samples collected at the first or third trimester, exhibiting similar gestational weight gains, co-cluster. Permutational multivariate analysis of variance (PERMANOVA) tests will assess the degree of overlap between samples exhibiting low gestational weight gain versus samples exhibiting high gestational weight gain. A lack of clustering in the first trimester, followed by clustering of samples on the basis of similar gestational weight gain would indicate that alterations in the maternal microbiota during the course of pregnancy, impacts gestational weight gain. Next, we will attempt to correlate changes in the alpha diversity (as measured by the Shannon and Simpson indices) of the gut microbiome samples between the first and third trimester, with gestational weight gain. A decrease in alpha diversity (indicative of dysbiosis) associated with low gestational weight gain, would again indicate that dysbiosis is associated with maternal weight gain. To examine the influence of individual taxa on gestational weight gain, we will perform bivariate analyses that examine the correlation (Pearson, Spearman) of each taxon with gestational weight gain. Correlations will examine taxon abundance in first and third trimester, in addition to the change in abundance between the two trimesters. The Benjamini-Hochberg procedure will be applied to correct p-values while controlling for false-discovery rates.

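### The primary correlations and PERMANOVA on gestational weight gain are unadjusted for enrolment BMI in a cohort recruited by BMI group, so group differences can create or mask an association

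*Protocol*

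**What the plan says.** Recruitment is by BMI group. Section 4.2 states: "Our goal is to recruit 200 participants with normal BMI and 200 participants with low BMI into the study". Sections 4.2 and 5.4 define the groups by BMI when the woman is recruited and let normal-BMI women fill any shortfall. The synopsis dates the same grouping differently: "200 subjects with low BMI (less than 18.5) at conception".

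GWG is the weight change from MV1 to MV2 (section 3). Section 9.4.1 addresses the first primary objective in three main ways:

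- A PERMANOVA compares low-GWG with high-GWG samples. No covariate is named.
- For diversity: "Next, we will attempt to correlate changes in the alpha diversity (as measured by the Shannon and Simpson indices"), from first to third trimester, with GWG.
- For taxa: "we will perform bivariate analyses that examine the correlation (Pearson, Spearman) of each taxon with gestational weight gain". This uses abundance in each trimester and the change between them, with Benjamini-Hochberg correction.

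The power calculation in section 9.1 rests on one simple correlation of the Shannon index with weight gain, with no BMI term: "Assuming 400 participants are recruited into the study, and a type I error rate of 0.05, there will be 80% power to detect a" correlation above 0.14.

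Other text comes near to adjustment. Section 9.3 will try to add further nutritional measures as covariates where suitable, without naming BMI or these correlations. Section 8.1.2 mentions PERMANOVA-S, which can handle confounders, for community structure, and names no confounder. Table 8 lists maternal BMI, which can enter the complementary Similarity Network Fusion and Random Forest models of section 9.4.1.

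**The concern.** Enrolment BMI is a candidate common cause. Section 8.2 expects women with poor nutritional status at the start of pregnancy to show more dysbiosis throughout it, which links BMI group to the exposure. If BMI group also relates to GWG, the pooled correlation combines the within-group association with the difference between group means. The second part can be non-zero when the first is zero.

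Section 9.4.1 reads an association as evidence about dysbiosis and weight gain, and reads one clustering pattern as showing that changes in the microbiota affect weight gain. Without adjustment, such a finding might only restate that thin and normal-weight women differ. If the two group differences run in opposite directions, a real association could be hidden. Benjamini-Hochberg does not help, because the hypothesis it tests for each taxon is the confounded marginal correlation.

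The concern bears differently on the parts of the plan. The expectation in section 8.2 is about level, so it applies most directly to first- and third-trimester taxon abundances. A constant difference in level cancels in a change score, so the documents give less reason to expect a group difference in change in alpha diversity.

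**Working it through.** **1. The plan's own figure.** Inputs from section 9.1: N=400, alpha 0.05, power 80%. Sidedness is not stated; two-sided is assumed because it reproduces the figure. With the algorithm for one correlation used by the R package that section 9.1 names, the smallest detectable r is 0.1395, and power at r=0.14 is 80.3% (80.2% by plain Fisher z). The stated 0.14 reproduces. The significance threshold at N=400 is |r| = 0.098.

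**2. Correlation created by pooling.** Let p be the low-BMI share, and let dx and dy be the between-group differences in the microbiome measure and GWG, in within-group SDs. With zero correlation within each group:

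r = p(1-p)·dx·dy / sqrt[(1 + p(1-p)·dx²)(1 + p(1-p)·dy²)]

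Example, p = 0.5 and both differences 0.5: r = 0.25×0.25 / (1 + 0.25×0.25) = 0.0625/1.0625 = 0.059.

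The documents give neither dx nor dy, so these are assumptions over a range. Rejection rates are two-sided at n=400 with 200 per group, using the power function of step 1:

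| GWG difference (SD) | Microbiome difference (SD) | Induced r | Rejected |
|---|---|---|---|
| 0.2 | 0.2 | 0.010 | 5.4% |
| 0.3 | 0.3 | 0.022 | 7.2% |
| 0.5 | 0.1 | 0.012 | 5.7% |
| 0.5 | 0.2 | 0.024 | 7.7% |
| 0.5 | 0.3 | 0.036 | 11.1% |
| 0.5 | 0.5 | 0.059 | 21.7% |
| 0.8 | 0.5 | 0.090 | 43.7% |
| 0.8 | 0.8 | 0.138 | 79.1% |

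Equal differences of about 0.66 SD reach the significance threshold on average. About 0.81 SD is needed to reach r=0.14.

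**3. Does the 200/200 target drive this?** Section 5.4 gives 49.7% normal and 29.8% low BMI in the source population, so the natural low-BMI share of the eligible range is 29.8/(29.8+49.7) = 37.5%. At that share, 0.5 SD in both gives r=0.055 and 19.7% rejected (against 21.7%), and 0.8 with 0.5 SD gives 39.7% (against 43.7%). The target adds little.

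**4. Effect of adjustment.** In 5,000 simulated datasets per scenario with no within-group association, the pooled test rejected 4.9%, 6.9%, 21.5% and 80.4% at equal differences of 0, 0.3, 0.5 and 0.8 SD. Adjusted for BMI group, it rejected 4.9%, 5.2%, 5.3% and 4.8%.

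**5. Masking.** With a within-group correlation of 0.14 and differences of 0.5 SD in opposite directions, pooled r = (0.14 - 0.0625)/1.0625 = 0.073, below the 0.098 threshold on average.

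**6. Power after adjustment.** One covariate costs almost nothing in degrees of freedom: if the partial correlation is itself 0.14, power is 80.1% against 80.2%. But if 0.14 is the pooled correlation and both differences are 0.5 SD in the same direction, the within-group correlation is 0.14×1.0625 - 0.0625 = 0.086, and power for it is about 41%.

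**The case against.** The strongest objection is that the headline diversity analysis uses change, while section 8.2 supports only a difference in level. That stands. Nothing in the documents supports a group difference of 0.3-0.5 SD in diversity change, and at 0.1-0.2 SD with 0.5 SD in GWG the rejection rate is only 5.7-7.7%. It does not reach the taxon analyses, which also use abundance at each visit.

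Second, the documents give no BMI-group difference in GWG and no direction for one, and small differences barely matter. This also stands. The rates count both directions, while section 9.4.1 counts only a fall in diversity with low gain as support, so pooling could as well hide the expected result.

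Third, the plan partly deals with BMI through sections 8.1.2, 9.3, Table 8 and the integrative models, and a covariate list is commonly left to a SAP. That would answer a complaint about missing detail. Here, however, the protocol states the method: the taxon correlations are bivariate, and none of those provisions adjusts them or the diversity correlation.

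Fourth, enrolment BMI and GWG share the MV1 weight, so adjustment is not neutral. This is a fair caution and a reason to fix the model in advance and report crude estimates beside the adjusted ones.

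Two stronger readings are not supported. A reader might infer that the 200/200 target creates the problem, but the rates are much the same at the natural BMI mix. A reader might also infer that adjustment raises power for free. That needs covariates that explain GWG but are unrelated to the microbiome measure, whereas the bias argument supposes that BMI is related to both.

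**Conclusion.** The point holds as a weakness in a stated method. The main tests of the first primary objective are pooled and unadjusted, in a cohort recruited on a variable that the protocol itself expects to relate to the exposure. Whether this distorts the result depends on BMI-group differences in both GWG and the microbiome measure, and the documents supply neither. On the assumed range, the effect goes from negligible at 0.2-0.3 SD to roughly four times the nominal error rate at 0.5 SD in both, and nearly nine times at 0.8 and 0.5 SD. These are conditional figures. They do not show that a positive finding would be false, and they should not be read as the expected error rate of the diversity-change analysis. The change is worth making because adjustment removes the artefact at almost no cost, using data already collected.

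**What to change.** In section 9.4.1:

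- Make the main analysis a linear model of GWG on the diversity or taxon measure, or the equivalent partial correlation, with enrolment BMI as covariate.
- Add gestational age at MV1 and the MV1-MV2 interval as precision covariates. Enrolment may run to 16 weeks and MV2 spans 30-34 weeks, so the interval can range from 30-16 = 14 to 34-10 = 24 weeks.
- Put the same terms in the PERMANOVA.
- Report the crude correlations alongside the adjusted ones.
- Note that enrolment BMI and GWG share the MV1 weight, so the BMI coefficient itself should not be interpreted.

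Also align the timing of BMI in the synopsis, which refers to conception, with sections 4.2 and 5.4, which use BMI at recruitment.

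The cost is wording and a few degrees of freedom. Weight, height, visit timing and gestational age are already obtained under the protocol. The change should be justified by validity, with no claim of added power.

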#### 9.4.2 ADDRESSING THE SECONDARY OBJECTIVES

This study has the following secondary objectives: 1) To link the maternal microbiome to dietary intake, with a focus on calories and macronutrients; 2) To integrate maternal anthropometric factors, morbidity and mortality with microbiome data to reveal key modulators (microbial taxa and metabolites) of dietary intake during pregnancy and the post-partum period; 3) To determine the impact of the maternal microbiome during pregnancy, including the exposure to pathogens and parasites, on the development of the infant microbiome; and 4) To investigate the maternal microbiome's exposure to pathogens and parasites, and the association with intestinal inflammation.

To assess these secondary objectives, we will employ general linear models. In a first approach we will perform PERMANOVA and probe the association of microbial community structure with the clinical variables. Pair-wise differences in microbiome structure between patient samples at similar time-points are defined by abundance-weighted pair-wise differences using the Bray-Curtis dissimilarity metric. DESeq2, a method for differential analysis of count data, will subsequently be applied to investigate both associations of specific taxa with the clinical variables, together with the strength of those associations. DESeq2 will utilize default settings, and q-values calculated with the Benjamini-Hochberg procedure to correct p-values while controlling for false-discovery rates. These analyses will reveal which clinical variables (including exposure to pathogens and parasites) correlate with the maternal microbiome from a taxonomic perspective.

To probe the association of clinical variables with the function of the microbiome, PERMANOVA and DESeq2 analyses will be performed replacing microbial community structure metrics with microbial community function metrics, specifically: 1) metatranscriptomic profiles; and 2) stool metabolomic profiles. Profile differences will be defined through Spearman rank differences for metatranscriptomic data and Euclidean distance metrics for metabolomic profiles. These analyses will reveal microbial genes, metabolites and pathways that correlate with clinical variables.

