#### 2.2.5 MARKER GENE SURVEYS COUPLED WITH ADVANCES IN NEXT GENERATION SEQUENCING PROVIDE UNPRECEDENTED INSIGHTS INTO MICROBIAL COMMUNITIES

To date, microbiome studies have largely relied on marker gene surveys (e.g. 16S rRNA sequences) to profile community structure and dynamics[61-63]. In a typical application, PCR reactions are used to amplify marker genes from a DNA sample. Sequencing is then performed to yield tens of thousands of sequences which are subsequently compared against a database of known marker genes to yield readouts of the abundance of each taxon in the sample. Key to this technology is the identification of a variable genetic region that allows unambiguous identification of taxonomy, flanked by highly conserved regions that allow universal primers to amplify the marker genes. For bacterial surveys, hypervariable regions of the 16S rRNA gene are typically targeted. Recently, [name] and [name], targeted 18S and 28S rRNA genes to perform equivalent surveys for eukaryotic microbes (Table 3)[64]. **In combination, 16S, 18S and 28S rRNA markers reveal the bacterial and eukaryotic components of the microbiome.**

Organism	Incidence in 44 children N (%)
Blastocystis	15 (34)
Cryptosporidium	12 (27)
Eimeriorina (unknown genus)	24 (55)
Giardia	14 (34) a
Trichomonas	37 (84)
Tritrichomonas	38 (86)
Pentatrichomonas	2 (5)
Trichomonad (unknown genus)	2 (5)
Tetramitia (unknown genus)	2 (5)

a. Clinical diagnostic test of 41 patients

**Table 3. Protozoa in children with severe acute malnutrition from Malawi using 18S biomarker technology and clinical diagnostics.**

---

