#### 8.1.2 PROFILING MICROBIAL COMMUNITY STRUCTURE

Microbial communities will be analyzed through 16S and 18S rDNA surveys using established methods that target the V4 region of the 16S rRNA gene to capture bacterial taxa [95-97] and the V4V5 region of the 18S rRNA gene to capture eukaryotic taxa. DNA library preps will include error-correcting barcodes[98] for multiplexing of samples. Sequencing will be performed to generate ~50,000 2x300bp paired end reads generated per sample. To define taxonomic diversity, species profiles from 16S and 18S rDNA data will be clustered to identify differences in community structure across samples. We will utilize the QIIME2 platform[99], MOTHUR[100], multivariate approaches such as Permutation Multivariate Analysis of Variance (i.e. PERMANOVA-S a method that can associate microbiome changes with outcome measures while accounting for confounders[101]) among other state of the art tools. Differences between groups in microbiome community structure will be tested by analysis of similarities (ANOSIM) and co-occurrence analysis[102]. To better define bacterial pathogen burden, we will apply TaqMan array card technology for the simultaneous detection of 19 common enteropathogens[103].

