##### **Microbiome Variables**

1. Maternal gut bacteria profile
2. Maternal eukaryotic microbe profile
3. Infant gut bacteria profile
4. Infant eukaryotic microbe profile
5. Maternal metabolomic profile of stool
6. Maternal metabolic pathway expression profile
7. Maternal bacterial gene expression profile

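### Section 9.4.2 fixes DESeq2 at default settings; on sparse 18S counts the default size factors will probably be undefined or rest on very few taxa

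*Protocol*

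**What the plan says.** Protocol section 9.4.2 (secondary objectives) first plans PERMANOVA on Bray-Curtis dissimilarities. DESeq2 "will subsequently be applied to investigate both associations of specific taxa with the clinical variables". The settings are then fixed: "DESeq2 will utilize default settings, and q-values calculated with the Benjamini-Hochberg procedure". The section gives no exception for 18S tables, no other size-factor estimator and no rule for zeros.

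Eukaryotes are in scope. Table 8 (section 9.4) lists "Maternal eukaryotic microbe profile" among the microbiome variables, with the infant counterpart, and section 8.1.2 describes the assay as targeting "the V4V5 region of the 18S rRNA gene to capture eukaryotic taxa".

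The only 18S prevalences in the document are in Table 3 of section 2.2.5, captioned "Protozoa in children with severe acute malnutrition from Malawi using 18S biomarker technology and clinical diagnostics". It lists nine groups in 44 children.

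**The concern.** A count model is a reasonable choice for 16S and 18S tables. The difficulty is the normalisation that comes with the default. By the definition of the method (general knowledge about DESeq2, not described in the protocol), each sample's size factor is the median, over taxa, of the sample's count divided by that taxon's geometric mean across samples. One zero makes the geometric mean zero and drops the taxon. If every taxon has a zero somewhere, no size factor exists and the default run stops with an error.

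Enteric eukaryotes are typically present in some people and absent in others, so an 18S table is where this is most likely to happen. The team would then have to choose another normalisation after seeing the data, for an analysis whose settings the protocol had stated in advance. If the run does go through on one or a few universal organisms, every eukaryote log-fold change is expressed relative to those organisms.

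**Working it through.** **Inputs.** Table 3 (section 2.2.5): number positive out of 44, with *Giardia* out of 41 by its footnote. Planned sample: 400 women (section 9.1), with DNA extracted at four maternal visits (section 8.1.1).

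**Step 1: reproduce Table 3.**

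| Group | Positive / tested | Recomputed % | Stated % | Without the organism |
|---|---|---|---|---|
| *Tritrichomonas* | 38/44 | 86.4 | 86 | 6 |
| *Trichomonas* | 37/44 | 84.1 | 84 | 7 |
| *Eimeriorina* | 24/44 | 54.5 | 55 | 20 |
| *Blastocystis* | 15/44 | 34.1 | 34 | 29 |
| *Giardia* | 14/41 | 34.1 | 34 | 27 |
| *Cryptosporidium* | 12/44 | 27.3 | 27 | 32 |
| Three further groups, each | 2/44 | 4.5 | 5 | 42 |

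All percentages reproduce. Every group is absent in at least six children, so with these nine groups alone the default size factors are undefined already at n = 44.

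**Step 2: carry the prevalences to the planned sample.** With independent samples, P(taxon non-zero in all m samples) = prevalence^m. For the commonest group:

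- m = 200: (38/44)^200 = about 2e-13
- m = 400: (38/44)^400 = 3.4e-26
- m = 400 at the upper 95% limit for 38/44 (94.8%): about 6e-10

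In 1,000 simulated tables of 400 samples with the nine Table 3 prevalences, none had a usable taxon.

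**Step 3: allow for eukaryotes outside Table 3.** Their prevalence is not given, so these values are assumptions:

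| Assumed prevalence | P(present in all 400) |
|---|---|
| 95% | 1e-9 |
| 99% | 0.99^400 = 1.8% |
| 99.83% | 50% |
| 99.9% | 67% |

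These are chances for one taxon, and one is enough for the step to run. When a single taxon present in every sample was added to the simulation, 0 of 1,000 tables failed.

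**Step 4: what the run means if exactly one taxon is universal.** Call its count in sample j c_j and its geometric mean g. The size factor is c_j/g, so the taxon's normalised count is c_j / (c_j/g) = g in every sample. It is constant and cannot be tested. Every other taxon's normalised count is g times its ratio to that organism. With a few universal taxa the dependence is milder but of the same kind.

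**The case against.** The strongest reply concerns the evidence. Table 3 is background from severely malnourished Malawian children, not from young women in Matiari. It covers protozoa only, mixes 18S with clinical diagnostics, and reports incidence with no detection threshold. The planned assay is aimed at eukaryotes generally, and the step runs if any one of them is universal. All of this stands. A reader might infer that the eukaryote analysis cannot be computed; the documents do not show that, because they contain no 18S count table and no prevalence for the study population.

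A reader might also infer that the 16S fold changes would be biased. Nothing in the protocol says how many bacterial taxa would be universal at about 50,000 reads per sample, so that inference has no figure behind it.

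Nor do the parasite objectives collapse. Section 9.4.2 also has Bray-Curtis PERMANOVA, section 8.1.2 adds TaqMan array cards for 19 enteropathogens, section 9.3 plans simple tests on the presence of pathogens, and exposure can enter as an explanatory variable without any 18S size factor. The primary taxon analysis in 9.4.1 uses correlations and is untouched.

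Finally, size-factor type is often left to an analysis plan, and section 8.2 promises up-to-date tools. This part of the reply does not stand: 9.4.2 does not leave the setting open. It fixes it, and a general statement about tools does not override it.

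**Conclusion.** The point holds as a likely risk. Section 9.4.2 prescribes a normalisation that needs at least one taxon with no zeros, and none of the nine groups in the only 18S figures shown qualifies. If prevalences in the study women resemble Table 3 and no other eukaryote is universal, the default DESeq2 run on 18S counts would almost certainly stop (chance of avoiding it about 3e-26 at 400 samples). If one or a few other eukaryotes are universal, it would run with normalisation tied to those taxa alone. Neither outcome is what a prespecified taxon analysis should deliver.

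The figures assume that the Malawian prevalences transfer, that samples are independent, and that a child counted as negative corresponds to a zero count. The scope is the DESeq2 component of the eukaryote analysis and nothing wider.

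**What to change.** In section 9.4.2, change the settings clause so that, for taxon count tables, DESeq2 uses its defaults except for size factors of type poscounts, or another named zero-tolerant normalisation. Benjamini-Hochberg control stays as it is.

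Two additions are optional: a prevalence filter, and a presence/absence analysis of rare eukaryotes under the same false-discovery control. A filter alone is not a substitute. At an illustrative 10% threshold, six of the nine Table 3 groups would be kept, and all six still have zeros.

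The cost is one sentence and a slightly different normalisation. Data, samples and software do not change. The sentence should be in place before the 18S counts are seen.
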